14.7 FOLLOW-UP OF PATIENT AFTER AE

The investigator is responsible for ensuring the follow-up of any patient who experiences an AE during the clinical investigation.

All AEs experienced by a patient, irrespective of the suspected causality, will be monitored until the event has resolved, any abnormal laboratory values have returned to baseline or stabilised at a level acceptable to the investigator and Medical Expert, until there is a satisfactory explanation for the changes observed.

In case of SAE, the investigator or an appropriate qualified physician must re-examine the patient at regular intervals until the event has resolved or stabilised at a level acceptable to the investigator and Medical Expert and/or until completion of the “Last Patient Last Visit”.

Further follow up information will be reported to Laboratoires THÉA.

14.8 MANAGEMENT OF PREGNANCY

In case of the investigator or an appropriate qualified physician is informed that a patient becomes pregnant while taking IMDs, she will be immediately withdrawn from the clinical investigation and she will be followed until the outcome of the birth is available.

A communication will be sent by the investigator to Laboratoires THÉA as soon as he/she has knowledge of the normal outcome. Conversely, if the outcome of the pregnancy meets the criteria of SAE (e.g spontaneous or therapeutic abortion, stillbirth, neonatal death, congenital abnormality, birth defect), the investigator should follow the procedure for reporting of AE/incident.

Handling of a pregnancy occurring throughout the investigation follows the same reporting procedure as per an AE/incident notification.

Upon medically confirmed pregnancy during the clinical investigation the investigator must:

- Report immediately (**maximum 24 hours**) the pregnancy status to Laboratoires THÉA by sending the incident form to [REDACTED] [REDACTED] The investigator must also complete the corresponding AE e-CRF page.
- Discontinue the IMD
- Perform / ensure assessment until delivery of a thorough investigation of the fetus

- Remain responsible for any medical advice he/she might sought thus making appropriate decision upon pregnancy
- Report to Laboratoires THÉA Follow-Up data / update(s) using the incident form.

14.9 LIST OF FORESEEABLE AES TOGETHER WITH THEIR LIKELY INCIDENCE, MITIGATION OR TREATMENT

According to the IMD leaflets, the following side effects are known: rare possibility of mild eye irritation and ocular redness.

When you use eye drops, you might experience disturbing symptoms such as burning sensation, stinging sensation, foreign body sensation in the eye and blurred vision for a short time.

14.10 LIST OF NON-REPORTABLE ADVERSE EVENTS

NA.

14.11 INFORMATION REGARDING THE IDMC

NA.

15 VULNERABLE POPULATION

This clinical investigation will not be conducted in children, or in any other vulnerable populations.

If the patient is not capable of giving consent, the written consent of the patient's legal representative will be required before participation in the clinical investigation (see section 13).

16 SUSPENSION OR PREMATURE TERMINATION OF THE CLINICAL INVESTIGATION

16.1 TEMPORARY HALT OF THE CLINICAL INVESTIGATION

The Sponsor may suspend the clinical investigation for any safety, ethical or administrative reason at any time. The investigator, IEC or CA may suspend or prematurely terminate participation at the investigational sites for which they are responsible.

As required by the Clinical Trials legislation, in the case of temporary halt of the clinical investigation:

- The Sponsor shall notify each country in which that clinical investigation has been temporarily halted within 15 days from the temporary halt of the clinical investigation with a justification.
- For safety concerns, the Sponsor shall notify all the country(ies) in which that clinical investigation is being conducted thereof within 24 hours.
- For an exceptional circumstance (e.g. COVID-19 pandemic), the Sponsor will follow the CAs' recommendations.

In case of restart after temporarily halted study, a notification will be made to the CA. In case of temporarily halt on safety grounds, this notification should be submitted as a substantial modification.

The communication of the relevant information should take place via the respective national procedures applicable to clinical investigations (until EU portal is fully functional).

16.2 EARLY TERMINATION OF THE CLINICAL INVESTIGATION

The Sponsor or the investigator has the right to terminate the clinical investigation for any safety, ethical or administrative reason at any time. As far as possible, this should occur after mutual consultation.

As required by the Clinical Trials legislation, in the case of early termination of the clinical investigation:

- The Sponsor shall notify each country in which that clinical investigation has been temporarily halted within 15 days from the temporary halt of the clinical investigation with a justification.
- For safety concerns, the Sponsor shall notify all the country(ies) in which that clinical investigation is being conducted thereof within 24 hours.

The communication of the relevant information should take place via the respective national procedures applicable to clinical investigations (until EU portal is fully functional).

The investigator, IEC or CA may prematurely terminate participation at the investigational sites for which they are responsible.

Should the clinical investigation be terminated prematurely, all investigational materials (IMDs, completed, partially completed, etc.) must be returned to the Sponsor or the Sponsor's representative as if the clinical investigation had been completed.

Laboratoires THÉA shall have the right to terminate the clinical investigation at any time on written notice to the investigator. Without in any way limiting this right, Laboratoires THÉA would normally only terminate the clinical investigation in the following circumstances:

- Occurrence of
 - new events related to the conduct of an investigation or the development of an IMD likely to affect the safety of patients, such as:
 - a SAE which could be associated with the investigation procedures and which could modify the conduct of the clinical investigation,
 - a significant hazard to the patient population such as lack of performance of an IMD used for the treatment of a life-threatening disease,
 - a major safety finding from a newly completed animal study/investigation (such as carcinogenicity),
 - a temporary halt of an investigation for safety reasons if the clinical investigation is conducted with the same IMDs in another country by the same Sponsor.
- If severe and/or serious AEs with the IMD in human or animal studies should indicate discontinuation of the clinical investigation.
- If Laboratoires THÉA should wish to discontinue the clinical investigation for commercial reasons.
- If Laboratoires THÉA had reasons to believe that the clinical investigation could not be satisfactorily completed, including, but not limited to, the reason that inadequate numbers of patients could be enrolled or insufficient investigational sites found within the necessary time.

16.3 REQUIREMENTS FOR PATIENT FOLLOW-UP AND CONTINUED CARE

In the case of temporary halt or early termination of the clinical investigation, the requirements for patient follow-up will depend on the circumstance of the temporary halt or early termination:

- For reasons not affecting the benefit-risk balance, according to the Sponsor recommendations, the investigator could decide if the patient may continue the clinical investigation as planned or if the patient should be withdrawn from the clinical investigation.
- For reasons of a change of the benefit-risk balance, the patient should be withdrawn from the clinical investigation and the IMD must be discontinued.
- For an exceptional reason (e.g. COVID-19 pandemic), each investigator has to decide whether the patient continued the clinical investigation when able to follow the CIP requirements safely or to withdraw the patient from the clinical investigation, based on his/her assessment of the benefit/risk ratio regarding the COVID-19 pandemic situation in his/her country/region and own investigational site, in accordance with the national/regional recommendations.

This concerns all patients still on-going in the clinical investigation at the time of temporary halt or early termination.

If a patient is prematurely stopping the IMD or should prematurely withdraw from the clinical investigation, the investigator must perform at least one premature discontinuation visit followed by one/several follow-up visits as decided by the Sponsor and according to the circumstances.

If possible and depending the circumstance, the premature discontinuation visit will be realized on site and the follow-visit(s) could be performed by phone.

If it is not possible, the premature discontinuation visit will be performed by phone-call and/or online video consultation. In this case and if current circumstances are favorable, at least one of follow-up safety visit should be performed onsite.

During the premature discontinuation visit/phone-call, the investigator has to:

- Collect AE/incident,
- Check the IMD compliance,
- Check the number of returned used and unused IMD,
- Instruct the patient to stop or to continue the IMD (depending on the reason as described above),
- Ensure the continuity of investigational disease medication (if appropriate),
- Perform evaluations described for the premature investigation discontinuation/final visit if possible (onsite visit),
- Prescribe to the patient the best appropriate treatment if needed,
- Collect information on concomitant medications changes.

If some follow-up visit(s) are required or if the premature discontinuation visit could not be realized on site, the investigator will have to schedule these phone-calls/visits. During this/these visit(s), the investigator has to:

- Collect AE/incident,
- Collect information on concomitant medications changes,
- Check the IMD compliance, if applicable,
- Check the number of returned used and unused IMD, if applicable,
- Perform evaluations described for the premature investigation discontinuation/final visit if not done at the premature discontinuation visit,

- Prescribe to the patient the best appropriate treatment if needed.

In any case, the requirements for patient follow-up will be described in more details in specific guidelines which will be provided to each involved persons (investigators, Investigational team, Hospitals etc...) and to Institutions if necessary (IEC, CA etc...). This could be done by submitting a notification (in case of emergency) and/or a substantial modification.

17 PUBLICATION POLICY

By signing the CIP, the investigator agrees that the results of the clinical investigation may be used for the purposes of national and international registration, publication, and information for medical and pharmaceutical professionals. If necessary, the CAs will be notified of the investigator's name, address, qualifications, and extent of involvement.

The data resulting from this clinical investigation will be the proprietary information of Sponsor. An investigator shall not publish any data (poster, abstract, paper, *etc.*) without having consulted with Laboratoires THÉA in advance.

At the end of the clinical investigation, Laboratoires THÉA will prepare a Clinical Investigation Report.

For any manuscript for publication prepared by Laboratoires THÉA, Laboratoires THÉA reserves the right to select the investigators who will be the authors to review the manuscript. Laboratoires THÉA will allow the selected investigators sufficient time for full review of the manuscript before publication.

SAF	Safety Set
SAP	Statistical Analysis Plan
SD	Standard Deviation
[REDACTED]	[REDACTED]
SOC	System Organ Class
SOP	Standard Operating Procedure
STEAE	Serious Treatment Emergent Adverse Event
[REDACTED]	[REDACTED]
TEAE	Treatment Emergent Adverse Event
TFL	Table, Figure, and Listing
WHO	World Health Organization
[REDACTED]	[REDACTED]

This document is confidential.

2. Introduction

This SAP is based on Clinical Investigation Plan (CIP) No. LT2769-004, Version 2.0 dated 09 APR 2024 and the electronic Case Report Form (eCRF) Version 1.0 dated 12 AUG 2024. The analyses follow the guidelines from the International Organization for Standardization (ISO) described in [ISO 14155:2020 Clinical investigation of medical devices for human subjects – Good clinical practice](#)**Error! Reference source not found.**

The SAP will be finalized prior to database lock. Any deviations from the SAP after database lock will be documented in the final Clinical Investigation Report (CIR).

The purpose of this SAP is to ensure that the data listings, summary tables and figures which will be produced, as well as the statistical methodologies that will be used, are complete and appropriate as per study design and objectives.

3. Study Objectives and Endpoints

The aim of this investigation is the comparison of T2769 with Hylo-Forte®.

3.1 Study Objectives

3.1.1 Primary Objective

The primary objective of the investigation is to demonstrate the non-inferiority of T2769 compared to Hylo-Forte® in terms of total ocular surface staining (Oxford score) in patients with moderate to severe dry eye syndrome (DES).

3.1.2 Secondary Objective

3.2 Study Endpoints

[figure not shown]
3.2.1 Primary Endpoint

The primary performance endpoint is the change from baseline (D1) in total ocular surface staining grade according to Oxford 0-15 grading scheme at D36 in the study eye.

This document is confidential.

Statistical Analysis Plan

[figure not shown]
Sponsor: Laboratoires Théa; Clinical Investigational Plan No.: LT2769-004

3.2.3 Safety Endpoints

The safety endpoints are:

- Treatment-Emergent Adverse Event (TEAE) by System Organ Class (SOC) and Preferred Term (PT) (separately for ocular and systemic TEAE).

This document is confidential.

Statistical Analysis Plan

Sponsor: Laboratoires Théa; Clinical Investigational Plan No.: LT2769-004

4. Study Design

This is a 5-week, international, multicentre, randomised, investigator-masked, 2 parallel groups (T2769 versus Hylo-Forte®) investigation. The clinical investigation design is confirmatory.

- Multicentre

The investigation will be performed in different sites in European Union (EU).

- Randomised

Eligible patients will be randomised on a 1:1 basis to T2769 or Hylo-Forte® respectively at the Randomisation Visit on Day 1 (Visit #2 - D1).

- Run-in period

Patients meeting the screening criteria will undergo a 7-10-days run-in period. During this period, all patients will substitute their current dry eye treatment with Hydrabak®, ophthalmic solution containing NaCl 0.9%. This period will allow to verify signs and symptoms of DES, and to facilitate the washout from the ocular surface of previous artificial tears treatment. Patients will instil 1 drop in each eye, from 3 to 6 times daily.

- Investigator-masked

A double-masked investigation design is not possible due to different commercial packaging between T2769 – Hylo-Forte®. However, the identity of the Investigational Medical Device (IMD) given to each patient will not be known for the masked investigator who is independently in charge of the ophthalmic examination. To this aim, the masked investigator will differ from the person who will record the used/unused IMDs. The masked investigator should not receive the returned IMDs from the patients and returned IMD must be stored in a different place from the IMD that have not yet been dispensed. Patients will also be trained to not report any information that could lead to unblinding in the diary and to the masked investigator.

- Exposure to the IMD

IMD will be administered by the patient every day from D1 until Visit 4 (included), one drop in each eye 3 to 6 times daily into the lower conjunctival sac of each eye.

No IMD instillation must be done at least 2 hours before Visit#3 and 4. However, the first instillation can be done any time after the patient has completed the randomisation visit.

There will be two treatment groups:

- T2769 (test medical device)
- Hylo-Forte® (comparative medical device)

The chosen comparator, Hylo-Forte®, of which performance has been demonstrated in the treatment of DES, is considered as a reference product.

- Investigation population

The study population will consist of patients with moderate to severe DES who have been treated with artificial tears for at least the last month prior to screening visit. It corresponds to the IMD target population.

- Treatment period

A 5-week treatment period allows to evaluate the therapeutic effect and to observe any potential safety issues.

This document is confidential.

Statistical Analysis Plan

Sponsor: Laboratoires Théa; Clinical Investigational Plan No.: LT2769-004

- Primary [REDACTED] endpoint [REDACTED]

The primary [REDACTED] endpoint [REDACTED] of this clinical investigation (Section 3.2) have been taken into consideration based on the clinical literature review. Consequently, these endpoints were designed to provide adequate and sufficient clinical evidence on the performance, safety and clinical benefit of T2769 in its intended use.

Four visits are scheduled during the course of the clinical investigation as presented below:

Visit#1 (Screening Visit): Day 1-10 to Day 1-7 (Run-in Period)

Visit#2 – D1 (Randomisation Visit): Day 1

Visit#3 – D15: Day 15 (± 1 day)

Visit#4 – D36 (Final Visit): Day 36 (± 3 days) or Premature Discontinuation Visit.

Visits should be performed at the same hour (± 2 hours) in the morning.

5. Analysis Sets

The following analysis sets will be considered:

- Enrolled set:

Enrolled set are all patients who have signed the informed consent form and had completed the screening visit (has been recorded in the eCRF).

- Safety (SAF) set:

All enrolled patients, having received at least one dose of IMD. Patients will be analysed according to the treatment received. Safety set will be the primary population for safety analysis.

- Intent-to-Treat (ITT) set:

All randomised patients. Patients will be analysed according to the treatment they were assigned to at randomisation.

- Full Analysis Set (FAS):

All randomised patients having received at least one dose of IMD, with at least one baseline and one post-randomisation performance assessment. Patients will be analysed according to the treatment they were assigned to at randomisation. The FAS will be the primary population for performance analysis.

- Per protocol (PP) set:

Subset of the FAS including patients without any major CIP deviations likely to seriously affect the primary outcome of the study. Patients will be analysed according to the treatment received. [REDACTED]

[REDACTED] The PP set will be considered as the secondary population and will be used for sensitivity analyses of the primary [REDACTED] performance endpoint [REDACTED].

6. Statistical Methodology

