6.1.5.4 Premature Discontinuation Visit during the clinical investigation

A patient who prematurely discontinues from the clinical investigation should have, if possible, a Premature Discontinuation Visit. This last site visit should take place as soon as possible after the patient stops taking IMD. All follow-up procedures and examinations scheduled to be performed at the final visit should be performed at the patient's premature discontinuation visit.

If the patient is tested COVID-19 positive during the course of the clinical investigation, the patient has to inform the investigator. Either the patient may continue the clinical investigation when he/she can follow the CIP requirements safely and in accordance with the national/regional recommendations or the patient may be withdrawn from the clinical investigation.

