6.1.5.5 Additional Follow-Up Visit(s) (after the end of the treatment)

NA

6.1.5.6 Adaptive Follow-Up of Patients Prematurely Withdrawn due to an Exceptional Circumstance (e.g. COVID-19 pandemic)

The benefit/risk ratio will be evaluated both by the Sponsor at global level (regulatory requirement) and by the investigator regarding the situation and local regulatory requirements in his/her country/region and in his/her own investigational site.

If the patient withdrew from the investigation due to an exceptional circumstance, and if an onsite visit was not authorised, a premature discontinuation visit by phone is required.

- Premature discontinuation phone call

- Check the IMD compliance with the patient.
- Instruct the subject to stop the IMD and keep used and unused IMD for later return.
- Ensure the continuity of artificial tears medication as per routine clinical practice.
- Collect AE/Serious Adverse Event (SAE), incidents and any changes in concomitant treatments.

- Plan a safety onsite visit 4 weeks later (± 7 days) and ensure that the patient understands all recommendations.
- Record the phone call and all information collected in the patient medical record.

- **Safety Follow-up visit on site**

During the onsite follow-up visit done 4 weeks (± 7 days) after the premature discontinuation phone call, the following procedures are required:

- Ensure that dry eye is well controlled.
- Check the IMD compliance with the patient.
- Record the number of the returned used and unused IMD (by the authorised unmasked delegate).
- Check that the patient had stopped the IMD and takes the new treatment, collect start and end dates of these medications.
- Collect AE/SAE, incidents and any changes in treatments.
- Record the visit and all information collected in the patient medical record.

If a safety onsite visit is still not possible, the follow-up will be done by phone or online video consultation and the patient is asked to return the used and unused investigation products later, when the situation improves or the pickup of the IMD directly from the patient will be organised. The compliance will be checked with the number of the returned used and unused IMD.

6.1.6 Equipment to be used for Assessing the Clinical Investigation Variables and Arrangements for Monitoring Maintenance and Calibration

A slit lamp will be used to measure the total ocular surface staining grade according to [REDACTED] Oxford 0-15 grading scheme.

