6.3.8 Number of Patients Required to be Randomised in the Clinical Investigation

It is planned to randomise 74 patients in order to have 68 evaluable patients (34 per group) for the FAS analysis.

Evaluable patients will be defined as randomised patients having received at least one dose of IMD and with at least one performance endpoint post-randomisation visit.

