6.4.1.2 Performance Measures

6.4.1.2.1 Ocular Surface Disease Index (OSDI) Questionnaire

The OSDI questionnaire (Schiffman et al., 2000; Miller et al., 2010) must be completed by the patient at the beginning of a visit before medical history information is collected or any investigation assessments are performed. The total OSDI score range on a scale from 0 to 100

6.4.1.2.3 *Ocular discomfort (VAS)*

Ocular discomfort (global evaluation for both eyes) will be assessed by the patient at D1, D15 and D36 visits according to the following:

“Please mark a vertical line (not a cross) on the horizontal line, indicating your level of ocular discomfort due to ocular dryness within the last 48 hours”. VAS will be a 100 mm line: 0 mm = No discomfort, 100 mm = Maximal discomfort.

6.4.1.2.4 *Dry eye related ocular symptoms throughout the day within the last 48 hours*

Patient will be asked: “How do you judge the severity of the following ocular symptoms throughout the day within the last 48 hours, excluding the symptoms you felt immediately after instillation?”

The severity of the following ocular symptoms will be assessed: burning/irritation, stinging/eye pain, light sensitivity, itching/pruritus, eye dryness feeling, tearing, foreign body sensation as follows:

0 = Absent

1 = Mild, present but not disturbing

2 = Moderate, disturbing, but not limiting with daily activities

3 = Severe, very distressing and interfering with daily activities

The ocular symptoms will be assessed in global for both eyes at D1, D15 and D36 visits. The value at D1 will be the baseline value.

6.4.1.2.5 *Slit lamp examination*

- Conjunctival hyperaemia

The level of severity of conjunctival hyperaemia will be scored [REDACTED] in each eye and at D1, D15 and D36 visits (see Section 19.4).

- Tear Break-Up Time (TBUT)

The tear film stability will be measured 3 times after the instillation of fluorescein. TBUT will be rapidly assessed and expressed in seconds. The sum of the 3 measures will also be expressed in seconds. TBUT will be measured in each eye and at D1, D15 and D36 visits.

- Ocular surface staining ([REDACTED] Oxford scale)

The total ocular staining grade using [REDACTED] Oxford 0-15 grading scheme will be assessed at D1, D15 and D36 visits by staining in corneal area by fluorescein and conjunctival areas (temporal and nasal) by fluorescein with a yellow filter.

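### Does the plan need a new rule on whether an early discontinuation-visit Oxford score counts as D36 in the primary model?

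*SAP*

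**What the plan says.** Protocol section 6.1.5 and SAP section 4 give the same schedule line for the last visit: "Visit#4 – D36 (Final Visit): Day 36 (± 3 days) or Premature Discontinuation Visit". Protocol section 6.1.5.4 asks for the discontinuation visit as soon as possible after the patient stops the device, and adds: "All follow-up procedures and examinations scheduled to be performed at the final visit should be performed at the patient's premature discontinuation visit". An Oxford score is therefore expected there, although protocol section 6.4.1.2.5 lists the score only by scheduled visit: "Oxford 0-15 grading scheme will be assessed at D1, D15 and D36 visits". The exception is withdrawal in exceptional circumstances when no site visit is allowed (protocol section 6.1.5.6). In that case "a premature discontinuation visit by phone is required", and no staining score can arise.

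The primary endpoint is the change from D1 to D36 in the study eye. The model in SAP section 6.3.1 has D15 and D36 as its time points. SAP section 6.1.3 handles missing values by the model and a second method whose name is blacked out, under a missing-at-random assumption.

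The full analysis set in SAP section 5 is: "All randomised patients having received at least one dose of IMD, with at least one baseline and one post-randomisation performance assessment". Protocol section 6.3.8 states: "It is planned to randomise 74 patients in order to have 68 evaluable patients (34 per group) for the FAS analysis". There, an evaluable patient has had one dose and is a patient "with at least one performance endpoint post-randomisation visit".

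**The concern.** Taken literally, the schedule line puts a discontinuation visit in the D36 slot. A score from, say, the second week could then be analysed as a five-week result. On the other side, the discontinuation visit has its own protocol section, the model is built on scheduled time points, and the SAP has a missing-data section for dropouts. That suggests an early stopper simply has no D36 value. Assignment by actual study day is a third possibility.

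The choices give different estimates from the same data, and they differ in who contributes. A patient whose only post-randomisation score comes from an on-site discontinuation visit before Day 14 belongs to the full analysis set and counts as evaluable. If that score is assigned to neither D15 nor D36, the patient adds no row to the model.

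Non-inferiority rests on one confidence bound compared with +2, so a choice made after unmasking could follow the result.

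**Working it through.** **1. What the visible text settles.** The schedule line says when final-visit procedures are done. It does not say how a score is labelled for analysis. Two other places treat the analysis visit as something derived: SAP section 6.2.1 counts attended visits as taken into the analysis, and SAP section 6.3.1 plots means by visit as defined for analysis. No definition is visible. The text around these places is incomplete:
- The SAP contents list section 6.1.2 on bias and confounding, but its body is not shown.
- Section 6.1.3 is partly blacked out.
- Section numbers run from 7 straight to 11.
- The protocol's abbreviation list defines missing at random, a term its visible body never uses.

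The absence of a rule therefore cannot be inferred.

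**2. How many patients could be affected.** The only attrition figure comes from the sample size:
- 74 − 68 = 6 patients, and 6/74 = 8.1%. As a check, 68/0.92 = 73.9, which rounds up to 74.
- These six are the allowance for patients who are not evaluable. A dosed patient with an on-site discontinuation score is normally evaluable, so already among the 68.
- Three early stoppers per arm within the 34 would come on top: (6 + 6)/74 = 16% in five weeks. That is an upper scenario, not an expectation.
- If one to three patients per arm had only an unassigned early score, 68 − 2 = 66 down to 68 − 6 = 62 patients would enter the model.

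**3. Precision.** The SD is not visible. For 34 per arm, margin 2, one-sided 0.025 and no true difference, back-solving gives an SD of 2.51–2.54 at 90% power and 2.90–2.94 at 80%. The 95% half-width is 1.96 × SD × √(2/34): 1.19 points at SD 2.5 and 1.38 at SD 2.9.

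**4. Average shift from counting the early score as D36.** Let k be the number of early stoppers in an arm (k_T for T2769, k_C for Hylo-Forte) and g the points by which the early score is worse than the D36 value implied under missing at random.
- True difference 0: shift = (k_T − k_C)/34 × g. For 3 against 3 it is 0. For 4 against 2 and g = 1 to 3, it is 0.06 to 0.18. For the extreme 6 against 0, it is 0.18 to 0.53.
- True difference +2, balanced stopping, share f of the difference already present at the early score: shift towards T2769 = k/34 × (1 − f) × 2. With k = 1 this is 0.03 (f = 0.5) or 0.06 (f = 0). With k = 3 it is 0.09 or 0.18.
- The other handling can err as well. If k stoppers on T2769 alone would be 2 points worse at D36 than missing at random predicts, leaving D36 missing is too favourable by 2k/34 = 0.06 to 0.18.

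Neither handling is uniformly safer.

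**5. Disagreement within one trial.** Simulation of the planned model (34 per arm, SD 2.5 or 2.9, correlation 0.6, random stopping, 6,000 trials per scenario) compared the two handlings on the same data. The second row is a benchmark: a two-sample comparison (40,000 trials per scenario) before and after deleting the same number of patients at random. Each cell gives 1 / 3 patients per arm.

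| Change | Estimate moves (95th percentile) | Verdict differs, true 0 | Verdict differs, true +1 |
|---|---|---|---|
| Swap the handling | 0.17–0.27 / 0.30–0.53 | 1.8–4.5% / 4.0–8.4% | 3.6–5.5% / 7.3–10.1% |
| Delete random patients | 0.21–0.24 / 0.37–0.43 | 2.6–4.1% / 5.3–7.7% | 4.8–5.2% / 8.5–9.5% |

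The rows are close. The disagreement mostly shows what happens when a few observations change in a trial of 68. It is not evidence of harm from the visit label.

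**6. When the choice is made.** SAP section 2 says "The SAP will be finalized prior to database lock". Protocol section 7 requires detailed methods before lock and unblinding. Protocol section 10 places the deviation review, done blind, before lock, and section 6.1.2.3 opens the randomisation list only afterwards. SAP version 2.0 is dated 07-FEB-2025, ahead of the planned completion in April 2025 (protocol section 6.3.6).

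**The case for a change.** The strongest case for acting is that this is a confirmatory non-inferiority trial, where early scores counted as D36 pull the arms together if a true difference exists. In the simulation at a true difference of +2, counting them as D36 gave a one-sided error of 2.6–3.0% with one stopper per arm and 3.5–4.9% with three, against 2.4–2.6% with D36 left missing. Settling the point would take one sentence and perhaps one further model run.

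The direction of that effect stands, and so does the ambiguity of the schedule line. The size depends on three stoppers per arm, which the documents do not support. The good error rate of the missing-D36 handling depends on stopping having been simulated as random. An added sensitivity analysis is not shown to improve on what is planned: a per-protocol analysis is already specified, the blacked-out method in SAP section 6.1.3 may address dropouts, and a further model brings a second verdict that may conflict with the first. Full analysis set membership is the same under either handling; only the contributing rows differ.

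**Conclusion.** No change to the plan follows. The schedule line is loose, but this is a detail that analysts settle when they derive analysis visits, and the rule may already stand in text withheld from the public version. The documents call for methods to be fixed before lock and unmasking, and nothing visible suggests a later choice. Anyone holding the full SAP can check how the analysis visit is defined.

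The expected effect is small against a margin of 2 and a half-width of about 1.2 to 1.4 points: no average shift with balanced stopping and no true difference, and 0.03 to 0.18 points with one to three stoppers per arm at a true difference of +2. Only strongly one-sided stopping, such as 6 against 0, brings it to about half a point. All of this rests on assumed SD, numbers of stoppers and score gaps. The simulated rates of differing verdicts also assume a correlation of 0.6, and should not be read as a measure of harm. Which handling is preferable depends on how stopping treatment is meant to count, and the visible text does not decide that.
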